CONFIDENTIAL

TITLE PAGE

Division: Worldwide Development
Information Type: Clinical Protocol

Title:	[A Phase II Open-Label, Two-Arm Study of the MEK Inhibitor, Trametinib, To Investigate the Safety and Anti-Cancer Activity in Subjects with Melanoma with BRAF non-V600 Mutations]
---------------	--

Compound Number(s): GSK1120212

Vanderbilt-Ingram Cancer Center (VICC) Coordinating Center Protocol Number: VICC MEL 1457

Development Phase: II

Description: This study is a Phase II, open-label, multi-site two-arm study designed to determine the activity and safety of orally administered MEK inhibitor trametinib (GSK1120212), in subjects with melanoma harboring mutations in *BRAF* at locations other than codon 600 (BRAFnonV600^{MUT}) or BRAF fusions. The study will also evaluate the effect of therapy on tumor biomarkers. All patients will receive trametinib 2mg orally administered once daily. Cohort A will consist of subjects with melanoma harbouring mutations which have high or intermediate intrinsic catalytic activity and/or which previously been described sensitive to MEK inhibitors in pre-clinical and/or clinical studies (L597, K601E, G469A, E586K, F595L) as well as BRAF fusions. Cohort B will consist of subjects with melanoma harbouring mutations that have previously been shown to have low affinity for MEK phosphorylation and low intrinsic catalytic activity and/or low sensitivity to MEK inhibitors from previous studies (D594V, G466V, G496R etc), or for which the catalytic activity and effects on sensitization to MEK inhibitors is unknown. The primary endpoint is objective response rate to trametinib for patients in Cohort A; secondary endpoints include objective response rates in Cohort B, safety, progression free survival and overall survival in both treatment arms.

Subject: MEK inhibitor, trametinib, GSK1120212, BRAFV600 wild type, BRAF non-V600 mutant, NRAS wild type, cutaneous melanoma

Author(s): [name]; [name]; [name]; [name]

Copyright Novartis, 2015. All rights reserved. Unauthorized copying or use of this information is prohibited.

CONFIDENTIAL

COORDINATING CENTER / MEDICAL MONITOR INFORMATION PAGE

Medical Monitor and Sponsor Contact Information:

Role	Name	Day Time Phone Number	After-hours Phone/Cell / Pager Number	Fax Number	Address
Primary Medical Monitor	[name]				Vanderbilt-Ingram Cancer Center [name]

Appendix 2 : NYHA Functional Classification System.....	86
Appendix 3 : COCKCROFT-GAULT FORMULA.....	87
Appendix 4: ECOG Performance Status.....	88
Appendix 5 : Liver Safety Drug Restart Guidelines	89
Appendix 6 : QT interval on electrocardiogram corrected using the Bazett's formula (QTcB)	92
Appendix 7 : Medication Diary.....	93

CONFIDENTIAL

LIST OF ABBREVIATIONS

AE(s)	Adverse Event(s)
AJCC	American Joint Committee on Cancer
ALT	Alanine aminotransferase
ANCOVA	Analysis of covariance
ANOVA	Analysis of Variance
AST	Aspartate aminotransferase
AUC(0-∞)	Area under the concentration-time curve from time zero (pre-dose) extrapolated to infinite time
AUC(0-x)	Area under the concentration-time curve from zero (pre-dose) to some fixed nominal time x
AUC(0-t)	Area under the concentration-time curve from time zero (pre-dose) to last time of quantifiable concentration within a subject across all treatments
AUC(0-τ)	Area under the concentration-time curve over the dosing interval
β-HCG	Beta-Human Chorionic Gonadotropin
BP	Blood pressure
BPM	Beats per minute
BUN	Blood urea nitrogen
CBC	Complete blood count
CfDNA	Circulating cell free DNA
CI	Confidence Interval
CL	Systemic clearance of parent drug
CL/F	Apparent clearance following oral dosing
C _{max}	Maximum observed concentration
C _{min}	Minimum observed concentration
C _τ	Pre-dose (trough) concentration at the end of the dosing interval
CO ₂	Carbon dioxide
CPK	Creatine phosphokinase
CPMS	Clinical Pharmacokinetic Modeling and Simulation
CPSR	Clinical Pharmacology Study Report
CR	Complete response
CRO	Contract Research Organization
CRU	Clinical Research Unit
CSR	Clinical Study Report
CTA	Clinical Trial Authorization
CTR	Clinical Trial Registry
CV	Coefficient of variance
DBP	Diastolic blood pressure
DILI	Drug Induced Liver Injury
DLT	Dose-limiting toxicity
DMPK	Drug Metabolism and Pharmacokinetics
DNA	Deoxyribonucleic acid
ECG(s)	Electrocardiogram(s)
ECHO	Echocardiogram

CONFIDENTIAL

ECOG	Eastern Cooperative Oncology Group
eCRF	Electronic case report form
EDC	Electronic data capture
FDA	Food and Drug Administration
FTIH	First time in humans
GCP	Good Clinical Practice
GCSP	Global Clinical Safety and Pharmacovigilance
GGT	Gamma glutamyltransferase
HBsAg	Hepatitis B surface antigen
HIV	Human Immunodeficiency Virus
h/hr	Hour(s)
HR	Heart rate
HRT	Hormone replacement therapy
IB	Investigator's Brochure
ICH	International Conference on Harmonization
IDMC	Independent Data Monitoring Committee
IDSL	International Data Standards Library
IgM	Immunoglobulin M
IHC	Immunohistochemistry
IMP	Investigational Medicinal Product
IND	Investigational New Drug
INR	International normalization ratio
IP	Investigational Product
IRB	Institutional Review Board
IRC	Independent Review Committee
IU	International Unit
IV	Intravenous
IVRS	Interactive voice response system
Kg	Kilogram
L	Liter
LFTs	Liver function tests
LLN	Lower limit of normal
Ln	Naperian (natural) logarithm
LOQ	Limit of quantification
LLQ	Lower limit of quantification
LSLV	Last subject's last visit
LVEF	Left Ventricular Ejection Fraction
µg	Microgram
µL	Microliter
MedDRA	Medical Dictionary for Regulatory Activities
Mg	Milligrams
mL	Milliliter
MRS	Magnetic resonance spectroscopy
MRT	Mean residence time
MSDS	Material Safety Data Sheet

CONFIDENTIAL

Msec	Milliseconds
MTD	Maximum tolerated dose
MUGA	Multigated (radionuclide) angiogram
NCI-CTCAE	National Cancer Institute - Common Terminology Criteria for Adverse Events
NYHA	New York Heart Association
PD	Progressive disease or pharmacodynamic
PFS	Progression-free survival
PGx	Pharmacogenetics
PK	Pharmacokinetic
PR	Partial response
QC	Quality control
QTc	Corrected QT interval duration
QTcB	QT interval corrected for heart rate by Bazett's formula
QTcF	QT interval corrected for heart rate by Fridericia's formula
RAMOS	Registration and Medication Ordering System
RAP	Reporting and Analysis Plan
RBC	Red blood cells
RCR	Recommended Combination Regimen
RNA	Ribonucleic acid
RPED	Retinal Pigment Epithelial Detachment
RVO	Retinal Vein Occlusion
SAE	Serious adverse event(s)
SAS	Statistical Analysis Software
SD	Standard deviation or stable disease
SOP	Standard Operating Procedure
T	Time of last observed quantifiable concentration
t _{1/2}	Terminal phase half-life
T	Dosing interval
Tlag	Lag time before observation of drug concentrations in sampled matrix
Tmax	Time of occurrence of C _{max}
ULN	Upper limit of normal
UK	United Kingdom
UPC	Urine protein creatinine
US/USA	United States/United States of America
Vd/F	Apparent volume of distribution after extravascular (e.g., oral) administration
VICC	Vanderbilt-Ingram Cancer Center
WBC	White blood cells

Trademark Information

Trademarks of the Novartis group of companies
Mekinist

CONFIDENTIAL

1. INTRODUCTION

1.1. Background

Cutaneous melanoma is the most aggressive form of all skin cancers. Worldwide, it is currently expected that approximately 132,000 people will be diagnosed with melanoma each year and some 37,000 people are expected to die of the disease annually. Untreated, the median survival time for patients with Stage IV melanoma is approximately 6 months with 26% of subjects alive at 1-year (Korn 2008); the estimated 5-year survival rate is < 10% (Huncharek 2001). Median progression-free survival (PFS) is also short at 1.7 months and only 14.5% of subjects are progression-free at 6 months (Korn 2008).

Much has changed in the treatment landscape of cutaneous melanoma recently, but with the exception of ipilimumab, significant advancements have been made exclusively for patients with mutations in a specific locus of the BRAF protein (BRAFV600) that causes constitutive activation of the RAS/RAF/MEK/ERK (MAPK) pathway. BRAF is part of the RAS/RAF/MEK/ERK (MAPK) pathway, which is a critical proliferation pathway in melanoma. Normally, the MAPK pathway is activated by the binding of extracellular growth factors to membrane-bound growth factor receptors which then recruit intracellular proteins to the cell membrane, leading to the activation of the small guanosine triphosphate (GTP)-binding protein RAS. As a result, RAS adopts an activated conformation which in turn activates RAF, which phosphorylates MEK on two regulatory serine residues. Activated MEK then phosphorylates threonine and tyrosine residues on its only known substrates, the MAP kinases ERK1 and ERK2. Phosphorylated ERK dimerizes and translocates to the nucleus, where it plays a critical role in cellular proliferation, nuclear transport, deoxyribonucleic acid (DNA) repair, messenger ribonucleic acid processing, and translation.

Approximately 40% of cutaneous melanomas harbor a BRAFV600 mutation (BRAF V600^{MUT}). These mutations increase the intrinsic serine-threonine kinase activity of the BRAF protein (Davies 2002). The presence of a BRAF V600^{MUT} in a melanoma correlates with increased activity of, and functional dependence upon, the MAPK pathway. Most importantly, the presence of BRAF V600^{MUT} also correlates with clinical benefit in patients to treatment with small molecule inhibitors of the V600-mutant BRAF protein and MEK inhibitors. Vemurafenib (BRAFi, Genentech), dabrafenib (BRAFi, GlaxoSmithKline), and trametinib (MEKi, GlaxoSmithKline) have all gained regulatory approval for the treatment of stage IV or unresectable stage III melanoma patients with BRAF V600^{MUT} melanoma. However, these agents are not approved for use in patients without a mutation. As these patients represent > 50% of cutaneous melanoma patients, and a much higher proportion of patients with non-cutaneous melanomas, there is a critical need to identify additional effective therapeutic approaches.

Approximately 5% of all melanomas harbour mutations in BRAF in loci other than V600 (BRAF nonV600^{MUT}). These mutations are often not detected by many testing platforms which are commonly used in clinical practice that assess only codon 600. However, they are detected by testing platforms that assess for other regions of the *BRAF* gene that are known to be affected by somatic mutations, as well as platforms that sequence the entire *BRAF* gene. Many of these BRAF nonV600^{MUT} result in increased kinase activity of the

CONFIDENTIAL

BRAF protein in vitro (“high activity group” including L597V, K601E, G469A) (Wan 2004). In addition, other mutations that do not increase the catalytic activity of BRAF (“low activity/unknown” group, including G466E, D594V, G596R) (Wan 2004) appear to be able to increase MAPK pathway activity through protein-protein interactions with other components of this pathway. Furthermore, BRAF fusions have been recently identified in a small percentage of melanomas which activate MAPK signaling (Botton 2013; Hutchinson 2013). MEK inhibitors have demonstrated activity in vitro in melanomas with high activity non-V600 BRAF mutations and individual patients with these mutations have demonstrated significant clinical responses to treatment with MEK inhibitors. Thus, MEK inhibitors may have value as a targeted therapy in this population. Although there is evidence that low-activity BRAF mutations activate MEK and ERK signaling, the clinical benefit of MEK inhibition in melanomas with such mutations is poorly defined. In addition, multiple somatic mutations in BRAF have been identified that have yet to be functionally characterized (Wan 2004).

1.2. Trametinib

1.2.1. Trametinib Background

Trametinib is a potent, highly selective, allosteric inhibitor of MEK1 and MEK2, is non-competitive towards ATP, and inhibits both MEK activation and kinase activity. Trametinib interferes with cellular signal transduction and induces apoptosis in human tumor cell lines both *in vitro* and in xenograft mouse models. Activity was most extensive in cell lines and models that contained activating BRAF mutations (Gilmartin 2011; Jing 2012).

Trametinib was first dosed in humans in 2008 in MEK111054 (Infante 2012). This first-in-human study identified the recommended monotherapy dose for trametinib (2 mg once daily continuous dosing); established the safety, PK, and PD profiles; and demonstrated clinical activity in several tumor types including BRAF^{WT} melanoma (Falchook 2012). As of 23 June 2012, trametinib has been administered to more than 1700 subjects in 20 studies, including 10 monotherapy studies [Novartis, 2016. Trametinib was approved by the United States Food and Drug administration on 29 May 2013, under the brand name Mekinist, as a monotherapy in the setting of BRAFV600^{MUT} melanoma.

Trametinib has also been evaluated in combination with dabrafenib in BRAFV600^{MUT} melanoma. In BR113220, this combination appeared more efficacious than dabrafenib alone, prolonging progression-free survival and increasing objective response rates (Flaherty 2012) Although trametinib has been most extensively tested in BRAFV600^{MUT} melanoma, studies combining trametinib with other antineoplastic molecules are opening in other melanoma subtypes. The study described here is the first study in which trametinib or any molecularly targeted therapy will be evaluated specifically in BRAFnonV600^{MUT} melanoma.

CONFIDENTIAL

1.2.2. Pharmacokinetics of Trametinib in Humans

Peak plasma trametinib concentrations were observed 1.50 hours following single-dose administration of trametinib tablets under fasted conditions. The absolute oral bioavailability of the trametinib 2.0 mg tablet is moderate to high (72%) relative to a coadministered IV microdose [Novartis, 2016]. Trametinib is highly bound to plasma proteins (97.4%), has a high volume of distribution (Vd; 1060 L) and a long terminal half-life (5.3 days), and accumulates with repeat once daily dosing.

The metabolism of trametinib has been investigated using a series of *in vitro* and *in vivo* studies. Trametinib is metabolized via deacetylation to form M5 (deacetylation alone) and deacetylation in combination with mono-oxygenation to form M7 (mono-oxygenation and deacetylation). M5 can be N-glucuronidated to form M6 (N-glucuronidation of M5) while M7 undergoes O-glucuronidation to form M9 (O-glucuronidation of M7), a minor pathway in humans. Trametinib is metabolized predominantly via deacetylation (non-CYP450 mediated) alone or with mono-oxygenation or in combination with glucuronidation biotransformation pathways. Although the specific enzyme responsible has not been identified, deacetylation is likely mediated by hydrolytic esterases, such as carboxyl-esterases or amidases.

1.2.3. Clinical Safety of Trametinib

The adverse events (AEs) observed in the pivotal, Phase III registration study (Flaherty 2012) was consistent with that seen across trametinib monotherapy studies and is summarized here. The Phase III study demonstrated that the 2 mg, continuous, once daily dose of trametinib has an acceptable safety profile. Adverse events occurring in $\geq 15\%$ of subjects that received at least one dose of trametinib (N=211) were rash (57%), diarrhea (43%), peripheral edema (26%), fatigue (26%), dermatitis acneiform (19%), nausea (18%), alopecia (17%), and hypertension (15%). Less than 8% of the subjects had grade 3 or 4 rash (including only one patient with grade 4), and no grade 3 or 4 diarrhea was observed. Decreased ejection fraction or ventricular dysfunction occurred in 7% of the subjects, and $<1\%$ (n=2) had grade 3 cardiac-related events that were considered trametinib related and led to permanent discontinuation of the study treatment. Ocular events, most of which were grade 1 or 2, occurred in 9% of the subjects. Blurred vision was the most frequent ocular event (4%), and there was one case of reversible chorioretinopathy. Retinal vein occlusion, an AE that has been associated with MEK inhibitors, was observed only extremely rarely. Rash, diarrhea, visual disorders, hepatic disorders, cardiac-related AEs, and pneumonitis are considered AEs of special interest for trametinib because they are either known class effects (i.e. were observed with other MEK inhibitors) or are potentially life-threatening.

1.2.4. Clinical Activity of Trametinib

Trametinib has demonstrated significant clinical activity with an acceptable safety profile in Phase I-III studies (Falchook 2012; Flaherty 2012; Infante 2012; Kim 2013). In BRAFV600^{MUT} melanoma, the Phase III study of trametinib demonstrated improved rates of progression-free survival and overall survival (Flaherty 2012). In this study,

CONFIDENTIAL

trametinib demonstrated an overall response rate of 22% and a median PFS of 4.8 months. The duration of response was 5.5 months.

BRAFV600^{WT} melanoma has been evaluated in the trametinib first-in-human study (Infante 2012). This study enrolled 39 subjects with BRAFV600^{WT} cutaneous melanoma, of which 4 (10%) had confirmed objective responses (Falchook 2012). The median PFS for these 39 subjects was 2.0 months (95% CI 1.7-3.7 months; (Falchook 2012)). Subjects who were both BRAFV600^{WT} and NRAS^{WT} (n=20) had a higher response rate (20%) than those who were wild type only at BRAF (n=11; response rate= 0%). Moreover, a higher proportion of patients that were wild type for both genes, compared to those that were wild type for only BRAF, were on study treatment at week 24 (40% versus 18%; p=0.26) and at 1 year (30% versus 0%; p=0.07). Importantly, 2 patients with BRAFnonV600^{MUT} melanoma (L597V and G469A) were treated in this study with one achieving a partial response and the other with temporary stabilization of melanoma growth (see section 1.3.1). These results demonstrate that trametinib has clinical activity in subgroups other than BRAFV600^{MUT} melanoma.

1.3 Rationale in study population

1.3.1 Rationale for targeted therapy in BRAF nonV600^{MUT} melanoma

BRAF alterations in loci other than codon V600 occur in 4-6% of advanced melanomas in several published reports (Berger 2012; Dahlman 2012; Krauthammer 2012; Botton 2013). Some of these recurrent alterations constitutively activate MAPK signaling and may be exploited therapeutically. Direct inhibition of mutant BRAF with vemurafenib or dabrafenib appears ineffective in this population, although modest in vitro activity and a brief partial response have been reported for vemurafenib (Dahlman 2012; Bahadoran 2013). By contrast, in the preclinical setting and in occasional patients treated in clinical trials, MEK inhibition appears to be a more active therapeutic approach. For example, BRAF L597^{MUT} and K601E^{MUT} melanoma demonstrated in vitro sensitivity to trametinib (Dahlman 2012).

Clinical corroboration has been demonstrated by several patients who have achieved a response to MEK inhibitors. For example, a patient with BRAF L597S^{MUT} melanoma had a dramatic response to an experimental MEK inhibitor (TAK-733) (Dahlman 2012). Furthermore, in the phase I trial of trametinib, a patient with BRAF L597V^{MUT} melanoma experienced a prolonged partial response and remained on study for more than 2 years (Falchook 2012). An additional patient with a BRAF G469A mutation had a best response of stable disease. Finally, in a trametinib phase II study, a patient with BRAF K601E^{MUT} melanoma experienced a prolonged partial response (Kim 2013). MEK inhibition in this population has not been studied in a systematic fashion and has never been evaluated prospectively. There is strong rationale to systematically evaluate MEK inhibition in the BRAF nonV600E^{MUT} melanoma population as this is a significant subgroup without current approved targeted therapy options.

1.3.2 Rationale for study cohorts

Subjects with BRAF nonV600E^{MUT} melanoma may be further classified by the functional effects of each particular mutation on BRAF kinase activation and subsequent MEK

CONFIDENTIAL

phosphorylation. All well-characterized BRAF mutations in the kinase domain activate MAPK signaling, although the mechanisms vary. Many of the more common mutations, including V600, L597, K601 (see appendix 1 for full mutation list), robustly activate MAPK signaling through MEK phosphorylation and are predicted to be sensitive to MEK inhibition (Cohort A, “high activity”) (Wan 2004). However, other observed mutations including G469E and D594G may signal through other effectors which may confer resistance to MEK inhibition, although the clinical experience with these melanomas is extremely limited (Smalley 2009). Together with additional mutations of unclear significance, (including S467L and P731S), we have labelled this group as cohort B, the “low activity/unknown” group. Additionally, BRAF nonV600 mutations may occur coincidentally with activating NRAS or BRAF V600E mutations. The functional significance of these mutations is not clear. It is hypothesized that these play a secondary role in these tumors; therefore these patients will not be included in our study.

Insight into the relative frequencies of these groups can be obtained from a large group of melanomas which were subjected to whole exon sequencing as part of the melanoma TCGA effort. Among the first 266 tumors, all of which were primaries or metastases of non-acral cutaneous melanomas, 17 (6.3%) harbored somatic BRAF nonV600 mutations and were NRAS^{WT} and BRAF V600^{WT}. Of these, 10 (3.8%) could be classified as “high activity,” with the additional 7 melanomas (2.6%) in the “low activity/unknown” group (3 with low activity, 4 with unknown activity). Our primary study group of interest is cohort A: the “high activity” group, as there is known pre-clinical and clinical rationale to study this population. However, there may be additional patients who will benefit from trametinib in the “low activity/unknown” group (cohort B); therefore this group will also be eligible to receive therapy in an exploratory fashion.

Approximately 1% of melanomas harbor fusions in the *BRAF* gene. (Botton 2013; Hutchinson 2013). These rearrangements fuse the BRAF kinase domain with a partner gene which leads to constitutive activation of the MAPK pathway. BRAF fusions are a frequent recurrent event in pilocytic astrocytomas and other cancers and were recently identified in melanoma and melanocytic tumors (Ciampi 2005; Jones 2008; Palanisamy 2010). BRAF fusion melanoma appears to confer resistance to vemurafenib. By contrast, trametinib strongly inhibited MAPK signaling *in vitro* and is predicted to have clinical activity in BRAF fusions (Hutchinson 2013). Therefore, patients with identified BRAF fusions will be included in cohort A.

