3.5.2. Rationale for Population

Subjects with BRAFnonV600^{MUT} melanoma may respond to targeted therapy although as yet there have been no trial specifically enrolling this group. This patient population has an unmet medical need and trametinib monotherapy has achieved objective responses in such subjects. We are subdividing subjects based on the predicted activity of BRAF alterations into Cohort A (“high activity” BRAF mutations and BRAF fusion events) and Cohort B (“low activity/unknown” BRAF mutations) as defined by Wan et al published in Cell 2004; complete list is in appendix 1. This predetermined stratification will allow for improved definition of which subjects are likely to benefit from trametinib.

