Appendix 1 BRAF mutations by Cohort

Cohort A – “High Activity”*	Cohort B – “Low Activity/Unknown”	Excluded
R462I	G466E	Concurrent BRAF V600E mutation
I463S	G466V	Concurrent NRAS codon 12, 13, or 61 mutation
G464V	D594V	
G464E	G596R	
G466A	All other BRAF mutations	
G469A		
G469E		
N581S		
E486K		
F595L		
L597V		
L597S		
L597R		
L597Q		
T599I		
K601E		
A728V		
BRAF fusions/truncations		
*Defined by affinity for MEK phosphorylation in Wan et al, Cell 2004. Mutations with documented responses to MEK inhibitors are also included		

CONFIDENTIAL

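### G469E is in cohort B in Section 1.3.2 but in cohort A, the only tested cohort, in Appendix 1; Appendix 1 also has a probable slip, E486K for E586K

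*Combined protocol and SAP*

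**What the plan says.** **G469E.** Section 1.3.2 sets apart a group of alleles thought less likely to respond: "However, other observed mutations including G469E and D594G may signal through other effectors which may confer resistance to MEK inhibition". It adds mutations of unclear significance and concludes "we have labelled this group as cohort B". The cohort table in Appendix 1 lists G469E in the cohort A column.

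**E586K.** The description on the title page gives E586K as a cohort A example: "in pre-clinical and/or clinical studies (L597, K601E, G469A, E586K, F595L) as well as BRAF fusions". Appendix 1 does not list E586K. Its cohort A column has E486K, and its cohort B column ends with "All other BRAF mutations".

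**Standing of the list.** Section 1.3.2 refers the reader to Appendix 1 ("see appendix 1 for full mutation list"), and so does Section 3.5.2 ("complete list is in appendix 1"). No section says that Appendix 1 prevails where the texts differ.

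**Use of the cohorts.** Sections 13.1 and 13.3.2.1 apply the test (objective response rate, ORR, of at most 5% against at least 25%) to cohort A only. Cohort B has a futility stop at 0 of 15, but Section 13.3.2.2.1 reports its response rate descriptively, without a test.

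**The concern.** The allele list defines the primary analysis population: it decides who counts toward the first 15 and the total of 25 in cohort A. For G469E, the scientific rationale and the list contradict each other in current text. If the rationale is right, the tested cohort admits an allele that the protocol itself suspects of resistance, which would dilute the response rate. If the list is right, the rationale misdescribes the tested population. In either case a reader of the result could not tell from the protocol which population the 5% and 25% refer to.

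The E486K entry matters less. Followed literally, it would route an E586K patient to the descriptive cohort, against the description.

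**Working it through.** **1. The texts side by side**

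| Allele | Narrative text | Appendix 1 |
|---|---|---|
| G469E | Cohort B (Section 1.3.2) | Cohort A, listed by name |
| E586K | Cohort A (title-page description) | Not listed; cohort B through the catch-all if read literally |
| E486K | Not mentioned | Cohort A, listed by name |

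**2. Is E486K a slip?** The codons in the cohort A column of Appendix 1 run 462, 463, 464, 464, 466, 469, 469, 581, **486**, 595, 597 (four entries), 599, 601, 728. E486K is the only entry out of order, and it stands where 586 would fall. The example PCR panel in Section 3.3 covers codon 586 and not 486. The description names E586K. All three point to a one-digit slip. A misread digit in the PDF text cannot be excluded either.

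**3. The plan's own figures.** Inputs from Sections 13.1 and 13.2: stop at 0 of 15; reject with at least 4 of 25; null rate 5%, alternative 25%.

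- Early termination = (1 − p)^15. At p = 0.05 this is 0.4633; at p = 0.25 it is 0.0134. Table 20 has 0.463 and 0.013.
- P(reject) = Σ over x = 1 to 15 of Bin(x; 15, p) × P(Y ≥ max(0, 4 − x)), with Y ~ Bin(10, p). At p = 0.05 this is 0.0336; at p = 0.25 it is 0.9008. Table 20 has 0.034 and 0.901.

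The other rows of Table 20 also reproduce. The cohort conflict does not make the table wrong.

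**4. Illustrative dilution if G469E is wrongly in cohort A.** These assumptions are not in the documents: the other patients respond at 25%, G469E patients respond at a rate q of 0% or 5%, and on average k of 25 cohort A patients carry G469E. The blended rate is p = (1 − k/25) × 0.25 + (k/25) × q, which goes into the formula of step 3.

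| k | q | Blended p | Early termination | Power |
|---|---|---|---|---|
| 0 | – | 0.250 | 0.0134 | 0.9008 |
| 1 | 0% | 0.240 | 0.0163 | 0.8801 |
| 1 | 5% | 0.242 | 0.0157 | 0.8845 |
| 3 | 0% | 0.220 | 0.0241 | 0.8286 |
| 3 | 5% | 0.226 | 0.0214 | 0.8456 |

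The loss of power is about 0.016 to 0.021 for k = 1 and 0.055 to 0.072 for k = 3.

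**5. How many patients?** Section 1.3.2 gives group totals only: 10 high-activity and 7 low-activity or unknown among 266 tumours. There is no count per allele, so k is unknown and may be zero.

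**The case against.** The best defence is that an operating rule largely exists. Appendix 1 is a table headed by cohort, two sections call it the full or complete list, and Section 3.5.2 and the appendix footnote rest on the same kinase-activity paper. The sentence in Section 1.3.2 is tentative background and cites a different source. A coordinating centre would use the table. This stands as a description of likely practice. It does not remove the contradiction, and no sentence gives the appendix precedence.

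The footnote might seem to settle G469E, because "Mutations with documented responses to MEK inhibitors are also included". It does not. The allele-specific MEK-inhibitor responses described in Section 1.3.1 are for L597S, L597V and K601E. The remaining case there is no response: "An additional patient with a BRAF G469A mutation had a best response of stable disease". G469E is not among them.

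A reader might infer that E586K is a second conflict of equal weight. The evidence in step 2 does not support that; it is a probable typographical slip to confirm.

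A reader might also infer that one responder moved between cohorts could turn 4 of 25, which rejects, into 3 of 24, which does not. That does not fit the design. Section 3.5.2 calls the stratification predetermined, and Section 3.1 requires central registration before treatment. Cohort A enrols to 25 once stage 1 is passed, so a patient assigned to cohort B would be replaced. A 24-patient primary analysis would need reclassification after the fact, which the plan does not provide for.

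**Conclusion.** The inconsistency is real and the definition of the primary analysis population should be corrected. For G469E, Section 1.3.2 or Appendix 1 is wrong as written. The documents do not show which, and it should not be inferred that the appendix is the faulty one; that depends on the cited source. The E486K entry is a probable one-digit slip with a literal consequence for E586K.

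The likely effect is small. All patients receive the same treatment, inclusion criterion 4 admits both alleles, and Table 20 with its type I error of 0.034 stands. If G469E patients do respond less and are counted in cohort A, the effect is a loss of power: from 0.901 to about 0.880-0.885 with an average of one in 25, and to 0.829-0.846 with three, under the assumed 25% and 0% to 5% rates. If G469E belongs in cohort A, there is no such loss and only the rationale needs correcting. The number of affected patients is unknown.

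**What to change.** 1. Check G469E against the cited kinase-activity source, and make Section 1.3.2 and Appendix 1 agree.
2. Confirm that E486K in Appendix 1 should read E586K, and correct it.
3. Add one sentence: Appendix 1 governs cohort assignment, and the cohort is recorded at central registration.
4. If a patient with a disputed allele is already enrolled, report the cohort A response rate with and without that patient as a sensitivity analysis that does not replace the primary test.

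As a clerical matter only, the pointer in Section 3.1 to an appendix A should read Appendix 1.

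The cost is a few wording corrections and one added sentence. No extra patients or assays are needed, and Table 20 does not change.
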